For [Objective 2](#), that will compare patients who are being treated with dabigatran etexilate or VKA, a cohort design was selected to allow for comparisons between the two groups of patients regarding major and clinically relevant non-major bleeding events (primary safety outcome measure), and symptomatic recurrent DVT and PE events, including VTE-related mortality (primary effectiveness outcome measure). For the second objective, a balanced enrollment approach should be used so that the number of VKA patients does not vastly outnumber the dabigatran etexilate patients and both patient groups are collected at similar time points (i.e., for each dabigatran etexilate patient enrolled, the next VKA patient with the same index event (DVT/PE) should be recruited ideally at the same study site). Since the severity of the disease, treatment patterns and patient characteristics may differ considerably between patients with a DVT versus a PE, the treatment arms should have roughly equal numbers of patients with DVT and PE. To ensure global representation, regional recruitment caps will be employed to minimize under-or over-representation from a particular region. Patients should be enrolled ideally within 14 days but not more than 30 days of their acute VTE.

[figure not shown]

Figure 9.1:1 Study design

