The primary and further outcomes will be analyzed for dabigatran etexilate patients in comparison to VKA patients over 1 year. To support the sample size determination, assessments were performed for the primary safety outcome of major and clinically relevant non-major bleeding based on the observed event rate for VKA in the pooled analysis of the RE-COVER and RE-COVER II trials, and additional assumptions including a 1:1 ratio of dabigatran etexilate and VKA patients, one-year fixed follow-up, one-sided alpha of 0.025, and 15% loss to follow-up (Table [9.5:2](#)). With these assumptions, a total sample size of 5000

patients would provide 90% power to detect a hazard ratio of 0.69 between dabigatran etexilate and VKA.

Table 9.5:2 Sample size assessments for the primary safety outcome of major and clinically relevant non-major bleeding

Event rates		Hazard ratio	Power	Loss to follow-up	Total N
Dabigatran etexilate	VKA*				
5.3%	7.7%	0.69	90%	15%	5000
5.2%	7.7%	0.67			4500
5.1%	7.7%	0.65			4000
4.9%	7.7%	0.63			3500
4.7%	7.7%	0.60			3000

\* The VKA event rate is based on the pooled RE-COVER and RE-COVER II analysis of the oral treatment period [[P13-09153](#), [U12-3306-01](#)]. The Freedman formula was used for the calculations.

In combination with additional non-statistical considerations, a total sample size of up to 5000 patients (i.e., 2,500 patients per group) is deemed appropriate for the planned analyses for [Objective 2](#) on an exploratory basis. The actual power of the analysis will be dependent upon the actual rates of major bleeding and loss to follow-up in the current study, the covariates included in the statistical model, their degree of imbalance between the treatment groups, their strength of association with the outcome, and the use of propensity score matching, and may therefore be different.

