## **9.9 LIMITATIONS OF THE RESEARCH METHODS**

For Objective 1, a cross sectional design will be used to characterize the VTE patient population. Consecutive unselected enrollment will be employed to ensure that specific types of patients are not selected by site staff to participate. It is expected that accrual for this objective will occur rapidly as there are no requirements to ensure balance between the types of anticoagulation treatments prescribed. To ensure global representation, regional recruitment caps will be employed to minimize over- or under-representation from a particular region. There is also the potential that prescribing patterns may change for a variety of reasons such as antidotes for NOACs are approved for use.

For [Objective 2](#), two cohorts of patients (dabigatran etexilate vs VKA) will be followed for 12 months. VKA has been the mainstay of treatment of VTE for many years. It is widely available, affordable, but does require regular INR monitoring. Dabigatran etexilate is more expensive, may or may not be reimbursed, but does not require the continual INR monitoring. There are a number of different types of bias that could influence the analysis from these cohorts such as selection bias and recall bias.

The study is designed to collect new data. The entry criteria are non-restrictive which will permit the enrollment of a broad patient population. The choice of treatment is at the discretion of the investigator. Therefore the data collected in this study should reflect the treatment patterns and patient characteristics under conditions of routine clinical practice.

The primary safety outcome measure is major bleeding and clinically relevant non-major bleeding events (CRNMB) according to the ISTH definition. Clinically relevant non-major bleeding events and major bleeding events were combined in the phase III clinical trial safety analysis, and, although it is probable that clinically relevant non-major bleeding events may

be harder to detect, new recommendations for the ISTH are now available for reporting them in a consistent manner in a routine clinical practice setting. The enlargement of the main variable, in a validated and consistent manner, will maximize the efficiency of the clinical trial in order to not prolong excessively the study duration. As a result, the primary safety outcome measure will include major bleeding and CRNMB events and the sample size calculations have been adjusted accordingly.

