#### Selection bias:

Selection bias could occur at both the site level and the patient level. If sites where dabigatran etexilate is used frequently differ systematically with respect to patient or the routine procedures from sites that use dabigatran etexilate less frequently, the between site difference could lead to non-comparability between the dabigatran etexilate patients. To minimize the site level selection bias, a robust site feasibility process will be performed to ensure that the participating centers that have access to all available treatment options for VTE that are approved for use in that country and that those physicians follow the standard of care that is accepted within the country.

Selection bias at the patient level could occur if sites preferentially enroll specific patients into the study. To minimize selection bias at the patient level, at a minimum, dabigatran etexilate and VKA treatment options must be available. Consecutive unselected enrollment of patients will be used for the recruitment of patients into [Objective 1](#) which will address issues associated with preferential patient selection by the site staff however; this could potentially create other sources of bias. A balanced approach for enrollment will be used for [Objective 2](#). The balanced approach will also minimize effects of potential temporal changes in prescribing patients, as dabigatran etexilate and VKA patients are enrolled in similar time periods.

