Baseline variables will be included in the model based on their known/suspected association with the main outcome events. As suggested by the literature, only confounders or variables associated with the outcomes will be considered. Table 7.6: 1 summarizes the identified variables to be included in the logistic regression model based on these criteria. In the event of non-convergence, investigations will be done to explore the most likely reason and to aggregate or exclude the responsible variables. Generally, all missing values of variables which will be included in the logistic regression model will be imputed according to Section 6.6.

Table 7.6: 1 Variables for PS model

Variable	Comment	Potential for missing values and implications
Age group	<65, 65 to <75, >=75	Very unlikely
Sex	Male, Female	Rare
BMI	<18.5, 18.5 to <25, 25 to <30, 30 to <35, ≥35, missing	Missing will be imputed
Creatinine clearance	<30, 30 to < 50, 50 to <80, ≥80, missing	Missing will be imputed
Region	Europe, Middle East, North America, Latin America, Asia, Other	Very unlikely
Smoking status	non-smoker, current smoker, past smoker, unknown	Rare – will impute missing and unknown values
Alcohol use	Never, < 1 drink/week, 1-7 drinks/week, ≥8 drinks/week, unknown	Rare – will impute missing and unknown values
Trauma or surgery	True or False (CRF categories, medical history and concomitant diseases will be manually reviewed – 3 month time window)	N/A
Immobilization	True or False (CRF categories, medical history and concomitant diseases will be manually reviewed (past and concomitant))	N/A
Obesity	True or False (CRF categories, medical history and concomitant diseases will be	N/A

	manually reviewed (past and concomitant))	
Thrombophilia	True or False (CRF categories, medical history and concomitant diseases will be manually reviewed (past and concomitant))	N/A
Pregnancy and peri-partum period	True or False (CRF categories, medical history and concomitant diseases will be manually reviewed (3 month time window))	N/A
Concomitant use of aspirin	True or False (concomitant medication and other VTE therapies will be manually reviewed (concomitant))	N/A
Concomitant use of clopidogrel	True or False (concomitant medication and other VTE therapies will be manually reviewed (concomitant))	N/A
Estrogen therapy	True or False (concomitant medication and other VTE therapies will be manually reviewed (3 month time window))	N/A

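### Calendar period is absent from both the propensity and the sensitivity Cox models, although the protocol names temporal change as a bias and the recording of the primary safety outcome may have shifted in August 2017

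*SAP*

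**What the plan says.** **Adjustment.** In SAP (Objective 2) section 7.6 the main analysis is a Cox model weighted by overlap weights from the estimated propensity score, with no other covariate named. On the content of the score: "Table 7.6: 1 summarizes the identified variables to be included in the logistic regression model based on these criteria". The criteria are that a variable is a confounder or is associated with the outcomes. Table 7.6: 1 has 29 entries, including region and index event type. Table 7.6: 2, for the sensitivity Cox model, has 14 and omits region. Neither has a calendar-time term. Section 6.5 excludes centre from every analysis, and section 7.4 refers back to the protocol on bias.

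**Temporal change.** Protocol section 9.9, under selection bias, says of Objective 2: "The balanced approach will also minimize effects of potential temporal changes in prescribing patients". Section 9.1 describes the approach. It should be used so that "the number of VKA patients does not vastly outnumber the dabigatran etexilate patients" and so that the groups are collected at similar times, the next VKA patient with the same index event following each dabigatran patient. The same study site is asked for only ideally.

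**Dates.** Section 6 of the protocol gives 01 February 2016 as the actual start of data collection and 31 December 2018 as the planned end. Section 5 dates the addition of CRNMB to the primary outcome to 18 August 2017, and the same revision added its ISTH criteria to section 9.3.3. Version 3.0 is dated 01 September 2017.

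**The concern.** Period confounds the comparison only if it is linked both to treatment and to the recorded event rate.

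The protocol raises the treatment link itself. Its safeguard is a recruitment instruction to sites, and the analysis carries nothing over from it: there is no pairing, no centre and no period.

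The outcome link has support for bleeding. Section 9.9 of the protocol concedes that CRNMB may be harder to detect. It became part of the primary outcome roughly a year and a half into data collection, so it may have been recorded less completely before the change than after it.

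If the dabigatran share also moved over that time, the weighted hazard ratio for bleeding would absorb part of the difference. The balance table might not reveal this, because period is not among the listed model variables.

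**Working it through.** **1. The plan's own figure.** Protocol section 9.5 gives "additional assumptions including a 1:1 ratio of dabigatran etexilate and VKA patients, one-year fixed follow-up", "one-sided alpha of 0.025, and 15% loss to follow-up", the Freedman formula and the table row "5.3% 7.7% 0.69 90% 15% 5000".

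- VKA hazard: −ln(1 − 0.077) = 0.0801. Dabigatran hazard: 0.69 × 0.0801 = 0.0553. Loss hazard, spread over the year: g = −ln(0.85) = 0.1625.
- Probability of an observed event, h/(h+g) × (1 − exp(−(h+g))): VKA 0.0711, dabigatran 0.0497.
- Events: 2500 × (0.0711 + 0.0497) = 302.
- Freedman power: Φ(√302 × (1 − 0.69)/(1 + 0.69) − 1.96) = 89.0%, against the stated 90%. N = 5000 solves to a hazard ratio of 0.685, which rounds to 0.69.

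The design figure reproduces. The standard error of the log hazard ratio is 2/√302 = 0.115.

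**2. Bias from an omitted period, at a true hazard ratio of 1.** None of these inputs is in the documents:

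- Early share of person-time w = 0.57. This is about what uniform accrual from February 2016 to December 2017, 12 months of follow-up and a split at 01 September 2017 would give.
- Dabigatran share a (early) and b (late).
- Early/late recorded event rate r = 0.775 or 0.625.

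Observed ratio = [(w·a·r + (1−w)·b) / (w·a + (1−w)·b)] ÷ [(w·(1−a)·r + (1−w)·(1−b)) / (w·(1−a) + (1−w)·(1−b))].

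Worked case, a = 0.40, b = 0.60, r = 0.625:

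- Dabigatran: (0.1425 + 0.2580)/(0.2280 + 0.2580) = 0.824.
- VKA: (0.2138 + 0.1720)/(0.3420 + 0.1720) = 0.751.
- Ratio: 1.10.

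| Dabigatran share, early/late | r = 0.775 | r = 0.625 |
|---|---|---|
| constant (any value) | 1.00 | 1.00 |
| 45% / 55% | 1.03 | 1.05 |
| 40% / 60% | 1.05 | 1.10 |
| 55% / 45% | 0.98 | 0.95 |
| 60% / 40% | 0.95 | 0.91 |

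A second parameterisation gives the same order of size. Let A and B be the proportions of dabigatran and VKA patients enrolled in the later half, and q the later/earlier hazard ratio. The bias factor is (1 − A + A·q)/(1 − B + B·q). For q from 0.7 to 1.5 it runs from 0.965 to 1.041 at 0.55/0.45 and from 0.932 to 1.083 at 0.60/0.40.

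**3. What such a factor does at 302 events.**

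- Factor 1.05: 0.69 reads 0.7245. Power becomes Φ(√302 × 0.2755/1.7245 − 1.96) = 79%, down from 89%.
- Factor 0.95: the one-sided false-positive rate in favour of dabigatran at a true hazard ratio of 1 becomes Φ(−ln(0.95)/0.115 − 1.96) = 6.5%, up from 2.5%.

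**4. Would the balance check see it?** Under 40%/60%, the early fraction of person-time is 0.228/0.486 = 0.469 for dabigatran and 0.342/0.514 = 0.665 for VKA. The standardized difference is 0.196/√((0.249 + 0.223)/2) = 0.40, above the SAP's trigger of 0.25. Under 45%/55% it is 0.20, below the trigger. Either value appears only if period is put on the list.

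**The case against.** The strongest reply is that the design attacks the treatment–time link directly. The instruction to recruit the next VKA patient makes timing the point of the balance. The word ideally attaches to the site, and the phrase about outnumbering concerns the overall ratio; a constant 60/40 split causes no period bias. All of this is right. What remains is that the instruction is advisory and the visible plan does not check whether it was followed.

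A reader might infer that both main hazard ratios are confounded. The documents do not support that. They show no time trend for recurrent VTE, and the remark that "There is also the potential that prescribing patterns may change for a variety of reasons such as antidotes for NOACs are approved for use" sits in the Objective 1 paragraph and concerns prescribing, not event rates. Nor do the November 2016 changes help. The reversal-agent item alters what is recorded about that agent, not an outcome definition, and the Middle East is already a level of region in the propensity model. The log also does not say that CRNMB went unrecorded before August 2017.

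It can be said that the SAP deliberately restricts the score to confounders and outcome-associated variables, since a variable that predicts only treatment costs precision and can amplify residual confounding. That is a fair general principle, but the August 2017 change makes period a plausible confounder for the primary safety outcome, and the SAP gives no reason for leaving it out.

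Three limits stand. SAP sections 5.3, 6.4 and 7.7 are not in the available text, so a period analysis there cannot be excluded. The balance check covers covariates of interest, which is not expressly a closed list, and the protocol plans an interim comparability assessment. The shifts at 45%/55% are under half a standard error (ln 1.05 = 0.049 against 0.115), in an analysis the protocol calls exploratory.

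**Conclusion.** The omission is real and worth correcting. Neither variable list holds calendar time, while the protocol names temporal change and relies on advisory concurrent enrolment. The case rests mainly on the bleeding outcome; for recurrent VTE it is only a possibility.

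The documents do not establish that any bias exists. It is nil if enrolment was concurrent. On the assumed shares and recording rates, a true hazard ratio of 1 would read about 1.03 to 1.10, or about 0.98 to 0.91 with the shares reversed. The upper end is close to one design standard error (ln 1.10 = 0.095 against 0.115). The stated sample size, power and alpha are not in question.

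**What to change.** - Add calendar period of index diagnosis to Table 7.6: 1. Add it to Table 7.6: 2 as well, or stratify the sensitivity Cox model by it. Use half-years or a split at the August/September 2017 revision.
- Tabulate period by treatment group, and report its unweighted and weighted standardized differences with the other covariates.
- If period is judged not to be a confounder, state the reason in the SAP.

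Date of diagnosis is already collected (protocol section 9.3.1.1). Data collection from February 2016 to December 2018 with 12 months of follow-up leaves roughly two years of enrolment, hence four half-years and three degrees of freedom. There is a slight loss of precision if period turns out to predict treatment only. Period of diagnosis also captures only part of a recording change that falls within a patient's follow-up, so the remedy is partial for patients who straddle August 2017.

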#### Treatment Options

Anticoagulant therapy is the standard treatment for venous blood clots, preventing new blood clots from forming, and preventing existing blood clots from getting larger and leading to dissolution of the existing clot after successful treatment. Rapid anticoagulation will minimize the risk of thrombus extension and PE in patients with VTE. Treatment duration is determined by the individual patient's clinical presentation. There are a number of factors that influence the type of anticoagulant therapy and treatment duration, including: the presence or absence of one or more risk factors for VTE (i.e., major orthopedic surgery), the acuteness of the thrombotic condition, the risk of recurrence, the risk of bleeding including bleeding due to underlying conditions (e.g., cancer) and issues that can affect compliance (e.g., parenteral versus oral administration and the degree of medical monitoring necessary to ensure efficacy and safety of the treatment).

Current guidelines for the United States (American College of Chest Physicians antithrombotic guidelines) and Europe (European Society of Cardiology), for the acute treatment of VTE recommend the initial administration of a parenteral anticoagulant, usually a low-molecular-weight heparin (LMWH), unfractionated heparin (UFH) or fondaparinux for 5-10 days. Parenteral treatment is followed by treatment with an oral vitamin K antagonist (VKA) such as warfarin that is titrated to a target International Normalized Ratio (INR) of 2 to 3 or dabigatran etexilate or edoxaban. Alternatively rivaroxaban or apixaban may be started immediately or after 1 to 2 days of LMWH, UFH or fondaparinux. Both rivaroxaban and apixaban require dose increases over 3 weeks (for rivaroxaban) or 1 week (for apixaban).

Anticoagulation treatment should last at least 3 months. Longer treatment may be recommended depending on the nature of the initial event (i.e. DVT versus PE), the risk of recurrence and the risk for bleeding [[P12-01518](#), [P14-16368](#)]. Patients with an unprovoked acute VTE should also receive extended anticoagulation therapy assuming that they are not at high risk for bleeding [[P12-01518](#), [P14-16368](#)].

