Optimal treatment duration for acute VTE and the secondary prevention of recurrent VTE is not definitively known. The two terms “acute treatment” and “secondary prevention” are not precisely defined and might overlap. Current guidelines recommend treatment for 3 months over shorter treatment durations [[P12-01518](#), [P14-16368](#)]. An extended duration of anticoagulation treatment should be considered for those patients with the greatest risk of VTE recurrence, i.e., those with an unprovoked DVT and/or PE; recurrent VTE, co-morbidities, such as cancer, chronic inflammation of the peripheral veins, and a strong genetic pre-disposition to thrombosis.

For patients with a chronic risk of recurrent VTE, there is evidence that when oral anticoagulation therapy is stopped, the risk of recurrence will increase to pre-treatment levels [[P08-08095](#), [R09-4888](#)]. Therefore, the decision to continue treatment for prevention of recurrent VTE must consider the risk factors for recurrence as well as any risk factors for bleeding. The risk of bleeding increases in patients with a prior history of bleeding events, the presence of certain co-morbidities (e.g., gastrointestinal ulceration, inflammation or malignancy or other metabolic disorders that might alter hemostasis such as cirrhosis or chronic renal disease or concomitant medications that alter hemostasis (i.e. antiplatelet agents)). These risks must be reviewed periodically, and therefore, treatment decisions should be individualized and periodically reviewed.

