### **9.2.1 Inclusion criteria**

1. Written informed consent provided by the patient or the patient's legal representative in accordance with local regulations
2. Diagnosis of an acute DVT irrespective of location and/or PE (For objective 1, assessment of patient for study participation should be done ideally within 14 days but not more than 6 months after diagnosis of the acute VTE. For Objective 2, patient assessment should occur ideally within 14 days but not more than 30 days from diagnosis)
3. Age  $\geq$  18 years
4. For [Objective 2](#), the planned anticoagulation therapy should be for at least 3 months
5. For Objective 2, dabigatran etexilate and VKA patients should be available for follow-up data collection (clinic or via phone) at the specified timeframes

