#### 9.3.1.1 Baseline visit data points

The Flowchart (Table [9.3.1:1](#) and Table [9.3.1:2](#)) outlines all of the data points to be collected. No study procedures or data recorded in the EDC system should be performed unless the patient has consented to participate in the study or a waiver has been obtained in accordance with local regulations. As in any observational study, patients will be managed according to local clinical practice. The choice of treatment is solely at the discretion of the participating physicians. This means there are no additional medical or procedural risks to patients by

participating in this study. No additional medical procedures are required, over and above those that the patient would receive if not enrolled.

- Review of in- and exclusion criteria
- Demographic data will include year of birth, gender, race (as allowed by local regulations), insurance status
- Height, weight, blood pressure, and heart rate
- Available laboratory data (e.g., serum creatinine, hemoglobin, and INR)
- Information regarding the index VTE event including:
  - date of diagnosis,
  - risk factors for VTE (i.e., if the VTE was provoked or unprovoked),
  - clinical signs and symptoms and
  - the following variables based on objective testing (e.g. Venous compression ultrasonography, venography for DVT CT, MRI and any other examination that is deemed relevant per routine clinical practice for DVT diagnosis or ventilation-perfusion (V-Q) lung scan, pulmonary angiography or spiral (helical) computed tomography scan for PE):
    - Date of diagnostic testing
    - Location, extent and severity of venous thrombus
    - Impression or findings
- Treatment for VTE should include all treatment details including specific therapies provided for the event, start date(s) and stop dates (if applicable), dosage, planned treatment duration, and rationale for treatment choice.
- Medical history including current concomitant diseases, history of previous VTE (if any) risk factors (i.e., if the VTE was provoked or unprovoked) for VTE re-occurrence and risk factors for bleeding.
- Concomitant therapies that are being currently used by the patient including the name of the therapy and indication.

9.3.1.2 Hospital discharge or at 14 days after diagnosis of VTE event (whichever occurs later)

For [Objective 1](#), the additional data points will include:

- Any changes to the treatment for the VTE event
- Date of hospital discharge, if patient was admitted to hospital

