Concomitant cancer	True or False (CRF categories, medical history and concomitant diseases will be manually reviewed (concomitant))	N/A
Antiphospholipid antibody syndrome	True or False (CRF categories, medical history and concomitant diseases will be manually reviewed (concomitant))	N/A
Polycythemia	True or False (CRF categories, medical history and concomitant diseases will be manually reviewed (concomitant))	N/A
Hypertension	True or False (CRF categories, medical history and concomitant diseases will be manually reviewed (concomitant))	N/A
History of previous VTE	True or False (CRF categories, medical history and concomitant diseases will be manually reviewed (regardless of timing))	N/A
Diabetes mellitus	True or False (CRF categories, medical history and concomitant diseases will be manually reviewed (concomitant))	N/A
Heart failure	True or False (CRF categories, medical history and concomitant diseases will be manually reviewed (regardless of	N/A

	timing))	
History of major bleeding	True or False (medical history and concomitant diseases will be manually reviewed (regardless of timing))	N/A
Stroke	True or False (CRF categories, medical history and concomitant diseases will be manually reviewed (regardless of timing))	N/A
Chronic hepatic disease	True or False (CRF categories, medical history and concomitant diseases will be manually reviewed (concomitant))	N/A
Chronic renal disease	True or False (CRF categories, medical history and concomitant diseases will be manually reviewed (concomitant))	N/A
Index event	DVT, PE, DVT and PE (CRF)	Very unlikely
Prior gastrointestinal bleed	True or False (CRF categories, medical history and concomitant diseases will be manually reviewed (regardless of timing))	N/A
Venous insufficiency or varicose veins	True or False (CRF categories, medical history and concomitant diseases will be manually reviewed (concomitant))	N/A

Overlap of estimated propensity scores

Overlap is the degree to which the ePS of the two treatment groups have a shared range. It is typically best examined graphically but will also be quantified by treatment group using the Kolmogorov Smirnov procedures [4] as a key quantitative indicator of the degree of overlap. To depict overlap in this context, a mirrored bar chart and overlapping line graphs of the estimated ePS of the two groups will be employed. One or both group distributions may be depicted before and after trimming. The same figure will be produced for logit transformed ePS.

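### The propensity model leaves out two baseline disease descriptors that the study collects, provoked/unprovoked status and thrombus location/extent, so avoidable residual confounding of the recurrent-VTE comparison is possible

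*SAP*

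**What the plan says.** **Who enters.** Protocol 9.2.1 admits "Diagnosis of an acute DVT irrespective of location and/or PE", so DVTs at any site are pooled.

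**What is recorded at baseline.** Protocol 9.3.1.1 lists provoked/unprovoked status, "Location, extent and severity of venous thrombus", and, with the treatment details, "planned treatment duration, and rationale for treatment choice".

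**What the protocol says about recurrence.** Under Treatment Options, extended therapy is to be considered for "those patients with the greatest risk of VTE recurrence, i.e., those with an unprovoked DVT and/or PE", followed by recurrent VTE, certain co-morbidities and genetic predisposition.

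**How covariates are chosen.** Protocol 9.7.2.1 asks for risk factors for VTE or bleeding and for variables that affect the choice of drug. SAP (Objective 2) 7.6 says "only confounders or variables associated with the outcomes will be considered".

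**What is in the models.** Table 7.6: 1 has 29 variables. The index event appears as "DVT, PE, DVT and PE (CRF". Trauma or surgery, immobilization, pregnancy or peri-partum period, estrogen therapy and cancer are separate terms, as are thrombophilia, previous VTE and venous insufficiency. There is no provoked/unprovoked term and no term for thrombus location, extent or severity. Table 7.6: 2 (sensitivity Cox model, 14 variables) also lacks them, and lacks index-event type as well.

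**The concern.** A variable that predicts recurrence and also influences which drug is prescribed is a confounder of the effectiveness comparison. On the protocol's account, unprovoked status predicts recurrence, and Treatment Options says that VTE risk factors and recurrence risk influence the type of anticoagulant. Thrombus location and extent are plausible candidates too, because the study pools all sites, and the Medical Background section traces about 90% of pulmonary emboli to proximal leg or pelvic veins.

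If one drug is given more often to provoked or limited thrombosis, part of a difference in recurrence would reflect the disease rather than the drug. Protocol 9.9 accepts that unmeasured confounding may remain, but that does not cover these items, which are measured.

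Overlap weights from a logistic model bring the listed covariates close to exact balance. The balance check on those covariates will therefore look good whatever happens to the unlisted ones.

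**Working it through.** **1. The plan's own figure.** The documents give no figure for this point and no sample size for recurrence. The only sizing (Protocol 9.5) is for bleeding: 5000 patients, 90% power, hazard ratio 0.69, "one-sided alpha of 0.025, and 15% loss to follow-up". It reproduces, and covariate choice does not enter it:
- Hazard ratio 5.3/7.7 = 0.688. Freedman events = [(1 + 0.688)/(1 − 0.688)]² × (1.960 + 1.282)², about 309.
- With exponential loss of 15% over the year, event probabilities are 0.0711 (VKA) and 0.0496 (dabigatran), mean 0.0604. N = 309/0.0604, about 5120, within 3% of 5000.

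**2. Recorded items against model terms.**

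| Baseline item (Protocol 9.3.1.1) | Named by the protocol as a recurrence risk? | In Table 7.6: 1? | In Table 7.6: 2? |
|---|---|---|---|
| Provoked/unprovoked | Yes, first in the list | Only through components | Only through components |
| Thrombus location/extent/severity | No | Only as DVT, PE or both | No |
| Planned duration | No; described as following from recurrence and bleeding risk | No | No |

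**3. How far the components stand in for the flag.** This was simulated with 200,000 patients, assumed prevalences, and overlap weights from a model holding only the five provoking components:
- Unprovoked defined as none of the components: standardized difference 0.24 before weighting, 0.06 after.
- Investigator's label disagrees in 15% of patients: 0.25 before, 0.16 after.
- A factor unrelated to the components, as assumed for extent: 0.25 before, 0.25 after.

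Disagreement is plausible. Table 7.6: 1 counts past as well as concomitant immobilization, with no time window, so an old episode is coded True even when the index event was unprovoked.

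**4. Effect on the hazard ratio (all inputs assumed).** Let p₁ and p₀ be the weighted prevalence of an omitted binary factor in the dabigatran and VKA groups, and R its recurrence hazard ratio. The multiplier is approximately [p₁(R − 1) + 1] / [p₀(R − 1) + 1]. With p₀ = 0.50:

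| p₁ | R = 1.5 | R = 2.5 |
|---|---|---|
| 0.55 | 1.275/1.25 = 1.02 | 1.825/1.75 = 1.04 |
| 0.65 | 1.325/1.25 = 1.06 | 1.975/1.75 = 1.13 |
| 0.45 | 1.225/1.25 = 0.98 | 1.675/1.75 = 0.96 |
| 0.35 | 1.175/1.25 = 0.94 | 1.525/1.75 = 0.87 |

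**5. Against the plan's balance trigger.** SAP 7.6 considers re-estimating the model above a standardized difference of 0.25. By its formula, 0.62 versus 0.50 gives 0.12/√[(0.62 × 0.38 + 0.50 × 0.50)/2] = 0.12/0.493 = 0.24. An imbalance of 12 points would stay just under the trigger. With R = 2.5 the multiplier is 1.93/1.75 = 1.10.

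**6. Linking steps 3 and 4.** At 50% prevalence, a remaining difference of 0.06 is about 3 points and 0.16 is about 8 points. For R = 1.5 to 2.5 these give 1.265/1.25 = 1.01 to 1.795/1.75 = 1.03, and 1.29/1.25 = 1.03 to 1.87/1.75 = 1.07. The flag alone therefore tends to the lower part of the range. Location/extent has no such absorption.

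**The case against.** **The provoking factors are already in the model.** This largely stands. Protocol 9.3.1.1 itself equates VTE risk factors with provoked status, and step 3 shows the components removing much of the imbalance. The flag is a modest refinement; location/extent gains more.

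**The protocol does not call location or extent a driver of recurrence.** This stands. They are listed among Objective 1 descriptors in 9.3.2. The sentence "Longer treatment may be recommended depending on the nature of the initial event" goes on to specify DVT versus PE, which the model does contain, so it cannot support adding location. The case for location/extent rests on the selection rule and the pooling of all sites.

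**Planned duration may be partly set by the drug.** This stands, and it is a reason to keep duration out of the main model. A reader might infer that as-treated censoring at the end of planned therapy leaves early exit from the risk set unaddressed. The documents do not support that: Objective 2 requires at least 3 months of planned therapy, and SAP 7.6 plans intention-to-treat versions of both the incidence rates and the main Cox model. Those analyses do not remove baseline confounding by omitted variables, however.

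**Enrolment is balanced.** This stands in part. Protocol 9.1 pairs on index-event type, ideally within site, but not on provocation or extent.

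**The public text is incomplete.** SAP sections 5.3, 6.4 and 7.7 are not shown, and the covariates of interest for the balance check are not listed. These items may already be described or used for subgroups. That would not place them in the propensity model.

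**The analyses are declared exploratory.** This is true and limits the consequence, but effectiveness is still a primary outcome of Objective 2.

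**Conclusion.** The point holds as an avoidable gap in the covariate list. Two measured baseline descriptors that fit the plan's selection rule, most clearly unprovoked status, are missing from the main propensity model and from the sensitivity Cox model.

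A reader might go further and infer that the one-year effectiveness comparison remains confounded. The documents do not show this. Bias needs an imbalance between the groups after weighting, and no such data are given. Its direction is therefore unknown. The size of roughly 2% to 13% either way rests on four assumptions: a residual imbalance of 5 to 15 points, a recurrence hazard ratio of 1.5 to 2.5, 50% prevalence in the VKA group, and a single binary factor. The sample size is not affected.

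**What to change.** In SAP (Objective 2) 7.6:
- Add provoked/unprovoked status and thrombus location/extent, as coded on the eCRF, to Table 7.6: 1.
- Name both in the balance table and report their standardized differences before and after weighting.
- Add both to Table 7.6: 2, or state why they are left out.
- Keep planned treatment duration out of the main model. Report its balance by group and add it in one sensitivity model, read alongside the planned intention-to-treat analysis.

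The cost is SAP wording and a few more logistic terms, which up to 5000 patients can carry. No new data collection should be needed, since Protocol 9.3.1.1 already asks for these items. The eCRF itself is not shown, so coding and completeness are unknown. Where extent is incompletely recorded, it will need the planned multiple imputation or a missing category.
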